13.2 Statistical Analysis

Cohort 1

The primary analysis will compare the difference between the number of EBV-infected B cells at the end of the treatment and control periods. Specifically, for each patient, the number of EBV-infected B cells at the end of the placebo period will be subtracted from the number of EBV-infected B cells at the end of the treatment period. The mean of these differences in all patients will be calculated and these values will be used to form the test statistic for a paired t-test. If magnesium treatment does not work, the true mean difference will be 0. If magnesium lowers the number of EBV-infected B cells, the true mean difference will be less than 0.

To determine which participants will continue to Part II, we will evaluate the number of EBV infected B cells (by EBV FISH) in each patient after 12 weeks of oral magnesium and after 12 week of placebo. If a patient has a 3.16-fold or 68.35% reduction with oral magnesium as compared with placebo, then that patient's study participation will end. Those patients who do

not meet this outcome will proceed to Part II (IV magnesium). Participation in Part II will depend on the result for each individual patient. We have chosen a 3.16-fold (68.35%) reduction as this is equivalent to a 0.5 log decrease.

Contingent upon patient participation in Part II, secondary analysis will compare the numbers of EBV-infected B cells at the end of 12 weeks versus 24 weeks of oral supplementation.

Cohort 2

The primary analysis will compare the difference between the mean fluorescence intensity (MFI) of NKG2D on CD8+ T cells at the end of the treatment and control periods. Specifically, for each patient, the MFI for NKG2D at the end of the placebo period will be subtracted from the MFI for NKG2D at the end of the treatment period. The mean of these differences in all patients will be calculated and these values will be used to form the test statistic for a paired *t*-test. If magnesium treatment does not work, the true mean difference will be 0. If magnesium increased the surface expression for NKG2D on CD8+ T cells, the true mean difference will be less than 0.

To determine which participants will continue to Part II, we will evaluate the MFI for NKG2D in CD8+ T cells in each patient after 12 weeks of oral magnesium and after 12 week of placebo. If a patient has a 2-fold or greater increase with oral magnesium as compared with placebo, then that patient's study participation will end. Those patients who do not meet this outcome will proceed to Part II (IV magnesium). Participation in Part II will depend on the result for each individual patient.

Contingent upon patient participation in Part II, secondary analysis will compare the MFI for NKG2D on CD8+ T cells at the end of 12 weeks versus 24 weeks of oral supplementation.

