A Double-blind, Placebo-controlled, Crossover Study of Magnesium Supplementation in Patients with XMEN Syndrome

NIAID Protocol Number: 15-I-0161

Sponsored by: NIAID

Version Number: 9.0

Date: March 8, 2019

Principal Investigator: [name]

Study Staff Roster

Principal Investigator:

[name] Laboratory of Immunology (LI)/NIAID

Associate Investigators:

[name] LI/NIAID

[name] Laboratory of Host Defenses/NIAID

[name] LI/NIAID

[name], ScM, CGC LI/NIAID

[name] National Heart Lung and Blood Institute/
Cardiovascular and Pulmonary Branch

[name] Biostatistics Research Branch/NIAID

Study Coordinator:

[name] LCID/NIAID

Medical Advisory Investigator:

[name] LID/NIAID

Protocol Summary

Full Title:	A double-blind, placebo-controlled, crossover study of magnesium supplementation in patients with XMEN syndrome
Short Title:	XMEN syndrome and magnesium
Clinical Phase:	Phase 1 and 2
Conducted by:	NIAID/LI
Principal Investigator:	[name]
Sample Size:	n=20 (n=10 for each cohort)
Accrual Ceiling:	n=30
Study Population:	Patients \geq 6 years with X-linked immunodeficiency with magnesium defect and increased susceptibility to Epstein-Barr virus (EBV) infection and neoplasia (XMEN) syndrome. Subjects will be divided into 2 cohorts: Cohort 1 (high EBV): Subjects with baseline blood EBV viral load \geq 5,000 copies/mL or EBV log \geq 3.7 IU/mL. Cohort 2 (low/no EBV): Subjects with baseline blood EBV viral load <5,000 copies/mL or EBV log <3.7 IU/mL.
Accrual Period:	4 years
Study Design:	A randomized, double-blind, placebo-controlled, crossover study to evaluate the safety and efficacy of oral magnesium L-threonate in subjects with XMEN syndrome. In Part I, patients within each cohort will be randomized into 2 arms. Each arm will receive 12 weeks of either oral magnesium L-threonate or placebo followed by crossover treatment for another 12 weeks. Patients in cohort 1 who experience \geq 0.5-log reduction in the number of EBV-infected B cells and patients in cohort 2 who experience \geq 2-fold increase in NKG2D receptor expression on CD8 T cells during oral magnesium treatment as compared to placebo will have completed the study. Patients who do not meet these respective criteria will undergo a 2-week washout and transition to Part II in which they will be hospitalized to receive 3 days of IV MgSO ₄ . These patients will then restart escalating doses of oral magnesium and continue for 24 weeks, at which point participation will be complete.

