3.1 Description of the Study Design

Patients enrolled onto the study will be divided into 2 cohorts. Patients in cohort 1 (high EBV group) will have baseline blood EBV viral load \geq 5,000 copies/mL or EBV log \geq 3.7 IU/mL. Patients in cohort 2 (low/no EBV group) will have baseline blood EBV viral load $<$ 5,000

copies/mL or EBV log <3.7 IU/mL. The study will be conducted in 2 parts; for each patient, participation in Part II is contingent upon the outcome of Part I. Part I is a randomized, double-blind, placebo-controlled, crossover study to evaluate the efficacy of oral magnesium L-threonate compared to placebo. Following an initial washout of magnesium-containing supplements, patients within each cohort will be randomized into 2 arms (**Figure 5**). Arm 1 will receive 12 weeks of magnesium supplementation followed by 12 weeks of placebo. Arm 2 will receive 12 weeks of placebo followed by 12 weeks of magnesium supplementation. Magnesium supplementation will consist of escalating doses of daily, orally self-administered magnesium L-threonate.

After 24 weeks of study, patients who show a 0.5-log (3.16-fold or 68.35%) reduction in the number of EBV-infected B cells (cohort 1) or or a ≥ 2 -fold increase in NKG2D receptor expression on CD8 T cells (cohort 2) during oral magnesium treatment as compared to placebo will end study participation. Such patients may remain on oral magnesium after completion of the study under the supervision of a primary care physician. Patients in whom oral magnesium was not clearly effective will begin a 2-week washout and proceed to Part II. Such patients will be hospitalized to receive 3 days of IV MgSO₄ administered 3 times per day for a total daily dose of 30/mg/kg/day. Then they will restart escalating doses of orally self-administered magnesium L-threonate and continue for the remaining 24 weeks of the study.

Prior to magnesium supplementation, blood draws on 3 consecutive days will be used to establish baseline NKG2D expression on CD8+ T cells, numbers of EBV-infected B cells, EBV viral load and intrasubject variability. The number of EBV-infected B cells and other relevant measures will be recorded before and after each supplementation period. The investigator measuring NKG2D expression and the numbers of EBV-infected B cells by FISH (primary outcome measures) will be blinded to the treatment group.

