6.3 Part I: Oral study agent (Week 1 to Week 24)

Oral magnesium or placebo (Week 1 to Week 12)

On Day 0, patients will begin to self-administer the oral study agent according to the dose escalation scheme in section 5.4.2.

Dose escalation every 2 weeks (Weeks 2, 4, and 6, or until maximum tolerated dose is reached)

Prior to increasing the study drug dose the study staff will contact patients to review their medication administration, assess for AEs and approve escalation to the next dose. In addition, patients will be contacted 1 week after dose escalation to assess for AEs.

4-week follow-ups (Weeks 4 and 8 +/- 1 week)

Patients will come to NIH for clinical and research evaluations to include:

- Medical history and physical exam

Clinical laboratory evaluations:

- CBC with differential
- Acute care panel, mineral panel, hepatic panel
- EBV by PCR
- CMV by PCR
- CRP
- ESR
- Total and ionized serum magnesium
- TBNK
- Spot urine magnesium

Research assays:

- Intracellular free Mg²⁺
- EBV FISH
- RNA extraction
- NKG2D expression on CD8 T cells and NK cells by flow cytometry
- Storage of serum, plasma, and PBMCs

Week 12 (+/- 1 week)

At the conclusion of 12 weeks of study agent patients will return to NIH for the following evaluations:

- Medical history and physical exam
- EKG

Clinical laboratory evaluations:

- 24-hour urine collection for magnesium
- CBC with differential
- Acute care, mineral and hepatic panels
- Quantitative immunoglobins
- Lymphocyte phenotyping
- CMV by PCR
- EBV by PCR
- ESR
- CRP
- Total and ionized serum magnesium

Research assays:

- Intracellular free Mg²⁺
- EBV FISH
- RNA extraction
- NKG2D expression on CD8 T cells and NK cells by flow cytometry
- Storage of serum, plasma, and PBMCs

Crossover (Week 13-24 +/- 1 week)

To crossover (from magnesium supplementation to placebo or from placebo to magnesium supplementation), patients will return any unused study agent and begin dose escalation with a new oral agent (magnesium or placebo). Patients will be provided dosing instructions and a medication log for recording AEs (Appendix C).

Dose escalation every 2 weeks (2, 4, and 6 weeks after the start of crossover, or until maximum tolerated dose is reached)

Prior to increasing the study drug dose staff will contact patients to review their medication administration, assess for AEs and approve escalation to the next dose. In addition, patients will be contacted 1 week after dose escalation to assess for AEs.

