13.3 Sample Size Justification

For cohort 1, the primary endpoint is the difference between the absolute number of EBV-infected B cells (EBV FISH) after 12 weeks of magnesium supplementation and after 12 weeks of placebo. With 10 subjects, there is 90% power to detect 1.15 standard deviation change by the 2-sided paired *t*-test with type I error rate of 0.05. To evaluate EBV change over time, we will compare the absolute number of EBV-infected B cells at the end of the control period and at the end of the treatment period. We will report the mean change in EBV with 95% confidence intervals.

For cohort 2, the primary endpoint is the difference between the MFI for NKG2D surface expression on CD8+T cells after 12 weeks of magnesium supplementation and after 12 weeks of placebo. With 10 subjects, there is 90% power to detect 1.15 standard deviation change by the 2-sided paired *t*-test with type I error rate of 0.05. To evaluate NKG2D change over time, we will compare the MFI for NKG2D surface expression on CD8+ T cells at the end of the control period and at the end of the treatment period. We will report the mean change in NKG2D with 95% confidence intervals.

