13.4 Power calculation

Table 3 gives the detectable difference (EBV-infected B cells at end of magnesium – EBV-infected B cells or NKG2D surface expression at end of placebo) with various sample sizes. The differences shown in the table are functions of the standard deviation. For example, with 10 patients if the standard deviation of the differences is 1 there is 90% power to detect a true difference of 1.15. If the standard deviation is 2, there is 90% power to detect a difference of $2.3=1.15*2$. The values in the table are based on using a t-test for the analysis. **Table 3** gives the ratio of the difference to the standard deviation that can be detected with various sample sizes in each group to obtain 90% power. At the end of the study a paired *t*-test will be used to determine whether the difference in the number of EBV-infected B cells or NKG2D expression in CD8+ T cells between the period treated with magnesium and treated with placebo (number of EBV-infected B cells or MFI for NKG2D expression after 3 months of magnesium treatment – number of EBV-infected B cells or MFI for NKG2D expression after 3 months of placebo treatment) is different from 0.

Table 3. Detectable differences with various sample sizes with 90% power and 2-sided type I error rates of 0.05. The differences are shown as functions of the standard deviations

Total sample size (with half of subjects randomized to each sequence)	Difference/standard deviation
10	1.15
12	1.03
14	0.94
16	0.87
18	0.81
20	0.76

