13.6 Randomization within each cohort

Patients will be allocated to Arm 1 or Arm 2 using a permuted block design with block size of 20. This means that exactly 10 patients will be randomly assigned to each arm. The study statistician will provide the randomized list of arm assignments.

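### The primary crossover t-test has no period term, so a period effect would cost precision and, in an unequal sequence split, shift the estimate; adjusting for period costs about one point of power

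*Combined protocol and SAP*

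**What the plan says.** Part I is a two-period crossover with two sequences (section 3.1): "Arm 1 will receive 12 weeks of magnesium supplementation followed by 12 weeks of placebo", and Arm 2 takes the reverse order. The Protocol Summary plans 10 patients per cohort.

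For each cohort, section 13.2 takes the end-of-magnesium value minus the end-of-placebo value in each patient and averages over all patients; "these values will be used to form the test statistic for a paired t-test". Section 13.4 repeats this test. Section 13 mentions no period or sequence term and no period-adjusted sensitivity analysis.

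Section 13.3 says "With 10 subjects, there is 90% power to detect 1.15 standard deviation change". Section 13.4 explains the scale: "if the standard deviation of the differences is 1 there is 90% power to detect a true difference of 1.15". Table 3 assumes that half of the patients are in each sequence.

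Under a heading that refers to randomization within each cohort, section 13.6 says "Patients will be allocated to Arm 1 or Arm 2 using a permuted block design with block size of 20", giving 10 patients per arm. Section 13.7.2.2 takes patients who do not complete 24 weeks off study. Section 10.9 allows withdrawn patients to be replaced, but does not require it.

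**The concern.** Anything that moves the outcome between week 12 and week 24 regardless of treatment enters the magnesium-minus-placebo difference with opposite signs in the two arms. Call this period effect π (period 2 minus period 1). It adds -π to every difference in Arm 1 and +π to every difference in Arm 2.

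The paired t-test treats this systematic gap between the sequences as random scatter. The interval widens, and the absolute difference that can be detected grows. If the arms are unequal in size, the +π and -π terms do not cancel, and the estimate moves by an amount that the plan neither estimates nor reports. With 10 patients per cohort there is little reserve to absorb either effect.

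**Working it through.** **Inputs.** From the plan: n = 10 per cohort, two-sided alpha 0.05, 1.15 SD at 90% power, block of 20, half of the patients per sequence in Table 3. Assumed: π = 0, 0.25, 0.5 or 1.0, in units of the within-sequence SD of the differences; normal differences; a constant additive period shift.

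**1. The plan's own figure.** For a paired t-test, df = 9 and the noncentrality is d√n. At d = 1.15 this is 1.15 × √10 = 3.64, and power is 89.8%. Exactly 90% needs d = 1.155. For n = 10 to 20 the exact values are 1.155, 1.030, 0.938, 0.868, 0.811 and 0.765, against 1.15, 1.03, 0.94, 0.87, 0.81 and 0.76 in Table 3. The table reproduces.

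**2. Paired test with a period effect, 5:5 split.** The ten differences carry five shifts of -π and five of +π. The shifts cancel in the mean, but their sum of squares is 10π². The expected sample variance is therefore (9 + 10π²)/9 = 1 + (10/9)π². Power and type I error come from integrating over the noncentral chi-square distribution of the sample variance (df 9, noncentrality 10π²).

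**3. Period-adjusted test.** The estimate is the average of the two sequence means. Its standard error is (s/2)√(1/n1 + 1/n2), where s is the pooled within-sequence SD and df = 8. At 5:5 the standard error is s/√10, and π drops out.

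| π | SD of differences | Mean 95% CI width | Detectable at 90% power | Power at 1.15 | Type I error |
|---|---|---|---|---|---|
| 0 | 1.00 | 1.39 | 1.15 | 89.8% | 5.0% |
| 0.25 | 1.03 | 1.44 | 1.18 | 88.4% | 4.4% |
| 0.5 | 1.13 | 1.57 | 1.26 | 83.9% | 3.0% |
| 1.0 | 1.45 | 2.04 | 1.50 | 63.7% | 0.7% |
| Adjusted, any π | 1.00 (within-sequence) | 1.41 | 1.17 | 88.8% | 5.0% |

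All columns except power and type I error are in within-sequence SD units. The two tests have equal power at π of about 0.21.

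**4. What 1.15 means.** If SD means the SD of the pooled differences, power at 1.15 SD stays at about 90% or more. The loss then appears as a larger absolute difference: at π = 1.0, 1.15 × 1.45 = 1.67 within-sequence SD.

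**5. How often the split is unequal.** The number in Arm 1 among ten patients from a block of 20 is hypergeometric (20, 10, 10): 5:5 in 34.4%, 6:4 either way in 47.7%, 7:3 in 15.6%, and 8:2 or worse in 2.3%.

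**6. Effect of an unequal split.** With n1 patients in Arm 1 and n2 in Arm 2, the paired estimate shifts by π(n2 - n1)/n. At π = 0.5:
- 6:4: shift 0.5 × 2/10 = 0.10; power 77% or 90% by direction; coverage 96.3%.
- 7:3: shift 0.5 × 4/10 = 0.20; power 69% or 94% by direction; coverage 93.9%.

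Averaged over block-of-20 splits, the paired test's type I error is 5.0%, 4.7%, 4.0% and 2.5% for the four values of π. Its power at 1.15 is 89.8%, 88.2%, 83.1% and 62.7%, against 86.9% adjusted. The adjusted estimate is not shifted in any split that has patients in both arms.

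**The case against.** The strongest reply is that this is a preference about efficiency. The documents report no period effect, and nothing in them places π above the break-even point. At π = 0.25 the paired test loses 1.4 points of power at 5:5; the adjusted test gives up 1.0 point when π = 0. The large losses need a period effect of a full within-sequence SD, close to the treatment effect that the trial is powered for. At π = 0.5, coverage is at or above 95% in 5:5 and 6:4 cohorts, which together make up 82% of splits. Replacement of withdrawn patients may restore some balance. A period-adjusted sensitivity analysis alone could also be defended.

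All of this stands, and it limits the weight of the point. It does not remove the asymmetry: at 5:5, adjustment costs about 1 point if π = 0 and saves about 5 points at π = 0.5 and 25 at π = 1.0. Choosing it after seeing the data would be post hoc.

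A reader might infer that the paired t-test is invalid or inflates false positives. The documents do not support this: averaged over the planned allocation, type I error is at or below 5%, given no differential carryover and dropout unrelated to treatment. Nor is Table 3 miscalculated. Section 13.4 scales it to the SD of the differences, and on the pooled reading 1.15 is correct.

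**Conclusion.** The point holds as a low-cost improvement in precision and reporting, not as an error in the plan. Without a period term, the primary test in each cohort is exposed to a loss that depends on an unknown π: negligible at 0.25, about 6 points of power at 0.5 and about 26 at 1.0, measured at 1.15 within-sequence SD in a 5:5 cohort. In addition, a 6:4 cohort shifts the estimate by 0.2π and a 7:3 cohort by 0.4π. Section 13.6 makes unequal cohorts more likely than equal ones, contrary to the split that Table 3 assumes, and dropout can add to the imbalance.

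The figures rest on normal differences and a constant additive shift. They may not describe cohort 1, which analyses absolute cell counts. That the planned test is valid on average rests on two conditions that the plan does not secure: no differential carryover (section 6.3 describes no washout at crossover) and non-informative dropout. One might also read the period term as a remedy for carryover. It is not, and a period estimate from this design may itself contain carryover.

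**What to change.** - **Section 13.2:** in each cohort, make the primary analysis the period-adjusted crossover test. This is a two-sample t-test of within-patient period differences between the sequences (df = n-2), or the equivalent model with treatment, period and patient. Report the adjusted effect with its 95% CI, and keep the paired t-test as a sensitivity analysis. State that the period term does not correct for carryover.
- **Table 3:** restate it with df = n-2 under equal sequences (1.17, 1.04, 0.94, 0.87, 0.81 and 0.77 for n = 10 to 20), and define SD as the within-sequence SD.
- **Section 13.6:** replace the block of 20 with an even block size that divides 10, so that a full cohort is 5:5.

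**Cost:** wording, one table and the randomization list; no new data. With no period effect, power at 1.15 SD falls from 89.8% to 88.8% at 5:5. The balance step belongs to the fix. Without it, adjusted power is 87.6% at 6:4, 83.0% at 7:3 and 72.2% at 8:2, and on average adjustment gains power only above a π of about 0.33 SD.

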13.3 Sample Size Justification

For cohort 1, the primary endpoint is the difference between the absolute number of EBV-infected B cells (EBV FISH) after 12 weeks of magnesium supplementation and after 12 weeks of placebo. With 10 subjects, there is 90% power to detect 1.15 standard deviation change by the 2-sided paired *t*-test with type I error rate of 0.05. To evaluate EBV change over time, we will compare the absolute number of EBV-infected B cells at the end of the control period and at the end of the treatment period. We will report the mean change in EBV with 95% confidence intervals.

For cohort 2, the primary endpoint is the difference between the MFI for NKG2D surface expression on CD8+T cells after 12 weeks of magnesium supplementation and after 12 weeks of placebo. With 10 subjects, there is 90% power to detect 1.15 standard deviation change by the 2-sided paired *t*-test with type I error rate of 0.05. To evaluate NKG2D change over time, we will compare the MFI for NKG2D surface expression on CD8+ T cells at the end of the control period and at the end of the treatment period. We will report the mean change in NKG2D with 95% confidence intervals.

13.4 Power calculation

Table 3 gives the detectable difference (EBV-infected B cells at end of magnesium – EBV-infected B cells or NKG2D surface expression at end of placebo) with various sample sizes. The differences shown in the table are functions of the standard deviation. For example, with 10 patients if the standard deviation of the differences is 1 there is 90% power to detect a true difference of 1.15. If the standard deviation is 2, there is 90% power to detect a difference of $2.3=1.15*2$. The values in the table are based on using a t-test for the analysis. **Table 3** gives the ratio of the difference to the standard deviation that can be detected with various sample sizes in each group to obtain 90% power. At the end of the study a paired *t*-test will be used to determine whether the difference in the number of EBV-infected B cells or NKG2D expression in CD8+ T cells between the period treated with magnesium and treated with placebo (number of EBV-infected B cells or MFI for NKG2D expression after 3 months of magnesium treatment – number of EBV-infected B cells or MFI for NKG2D expression after 3 months of placebo treatment) is different from 0.

Table 3. Detectable differences with various sample sizes with 90% power and 2-sided type I error rates of 0.05. The differences are shown as functions of the standard deviations

Total sample size (with half of subjects randomized to each sequence)	Difference/standard deviation
10	1.15
12	1.03
14	0.94
16	0.87
18	0.81
20	0.76

